Day/Month	PS	0	3	6	9	12	15	WD	18
Visit Number		1	2	3	4	5	6		7
medications related to cancer (e.g. pain medications, bone protective medications, spinal cord decompression surgery, palliative radiotherapy etc.)									
Reasons for discontinuation of ELIGARD® including AEs		X	X	X	X	X	X	X	X
AEs and SAEs Assessment ^h		X	X	X	X	X	X	X	X
Treatment for AEs and SAEs		X	X	X	X	X	X	X	X
PSA level, date and methods of test ⁱ		X	X	X	X	X	X		X
Serum testosterone level, date and methods of test ^j		X	X	X	X	X	X		X
Other laboratory Tests (if done within routine practice, last available value that is closest to each visit) ^j		X	X	X	X	X	X		X
Tumor evaluation/ Radiographic assessments and date of test ^k		X	X	X	X	X	X		X
Concomitant Medications Assessment		X	X	X	X	X	X	X	X
EORTC QLQ-PR25 (to be measured at baseline, 6 months, 12 months and at 18 months, mandatory) ^l		X		X		X			X
EQ5D-5L (to be measured at baseline, 6 months, 12 months and 18 months mandatory) ^l		X		X		X			X

Legend: X – required by protocol or if available in patient charts based on routine clinical practice. WD: withdrawl.

Footnotes:

- ^a The assessment of patient’s access to medical or surgical androgen deprivation therapy after the trial ends will be based on the interview by the physician at prescreening visit.

- b Demographic data - Date of birth (or age, if local regulations do not allow recording of patient's date of birth), Race as described by the patient (unless local regulations do not allow recording of patient's race), highest education level
- c Vital status – blood pressure, pulse rate, respiratory rate and weight. Height to be collected at baseline visit only
- d Baseline disease characteristics for prostate cancer - Time since diagnosis, Gleason score at initial diagnosis, Tumor, Nodes, Metastasis (TNM) classification, surgical history, biopsy results, dates and types of anti-neoplastic therapy including radiation therapy prior to study inclusion (including number of cycles, treatment duration, time interval since previous treatments), Eastern Cooperative Oncology Group (ECOG) status, bone lesions, soft tissue disease, visceral disease, pain.
- e Medical history – diabetes, hypertension, cardiac disorders
- f Prostate cancer status - stage of prostate cancer, bone metastasis, soft tissue disease, visceral disease, pain (using Visual Analogue Scale [VAS] 0-10 which will only be collected if done in routine clinical practice), ECOG status
- g ELIGARD® Use - ELIGARD® initiation and cessation.

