- h Adverse Events and Serious Adverse Events Assessment
 - Adverse Events (AEs)
 - Serious Adverse Events (Serious AEs) must be reported to the sponsor/ designee within 24 hours.
 - For this study, an ELIGARD® -related AE is defined as an adverse event in a patient administered ELIGARD® where a causal relationship is at least a reasonable possibility (drug event with either a possible or probable causal relationship), as determined by the investigator. Adverse events listed in the local label should be used by the investigator as reference safety information to understand whether an adverse event is expected with the use of ELIGARD®. This understanding should inform their causality assessments.
- i Prostate specific antigen (PSA) and Testosterone levels will be tested for all patients before ELIGARD® injection at each of the following visits: baseline, 3 months, 6 months, 9 months, 12 months, 15 months and at the follow up visit at 18 months. PSA progression must be confirmed by a second value obtained 3 or more weeks later. If PSA confirmation is not done based on standard clinical practice, the confirmatory PSA measurement will be performed at the next routine study visit.
- j Other laboratory tests (if done within routine clinical practice, last available value that is closest to each visit will be recorded) – Lactate Dehydrogenase (LDH), Alkaline Phosphatase (ALP), Hematology, Liver Function Test (LFT) and Renal Function Test (RFT)
- k Tumor Evaluation/Radiographic Assessments (if data available) – Computerized Tomography (CT) scan, Positron Emission Tomography (PET) Scan, Magnetic Resonance Imaging (MRI), Bone scan, X-ray, ultrasound or any other imaging test
- l European Organization for Research and Treatment of Cancer Quality of Life Questionnaire (EORTC QLQ-PR25) and EuroQol 5 Dimension 5 Level Health State Utility Index (EQ5D-5L) – to document whether completion of questionnaires was accomplished through self-administration or through the assistance of another person
- m A patient who discontinues from the study for whatever reason should have a follow up visit that will occur 3 months after the last administration of ELIGARD® for safety assessment. A patient that is unable to comply will be considered as a protocol deviation, provided that the reason for discontinuation is not due to patient's withdrawal of consent.

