2.3.2 Secondary Endpoints

- Efficacy outcomes of clinical response based on testosterone and PSA levels (Testosterone level and PSA will be assessed for all patients at each scheduled visit, prior to administering ELIGARD[®], and at the follow-up visit.)
- HRQoL assessment through QoL questionnaires – EORTC QLQ-PR25 (prostate cancer disease specific PRO) and EQ5D-5L (generic PRO) measured at 0, 6, 12, and 18 months.

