6 DISCONTINUATION

6.1 Discontinuation of Individual Patients

A discontinuation is a patient who enrolled in the study and for whom study treatment is permanently discontinued prematurely for any reason.

A patient is free to withdraw from the study for any reason, at any time, without reason for doing so and without penalty or prejudice.

A patient will be discontinued from the study in the case of:

1. Withdrawal of consent - patient decision to withdraw from further participation in the study
2. Patient safety is at risk (at the discretion of the treating physician)
3. Patient develops CRPC as determined by European Association of Urology (EAU) Prostate Cancer Guidelines 2016
4. Patient is lost to follow-up
5. Patient death during the study
6. Patient misses consecutive visit periods (window \pm 14 days) during the study
7. Patient who is less than 80% compliant with the dosage regimen for any 2 consecutive visit periods (window \pm 14 days) during the study.
8. Site terminated by the Sponsor
9. Study terminated by the Sponsor
10. Cessation of treatment with ELIGARD[®] (at the discretion of the treating physician). The reasons for stopping treatment will be noted (e.g., PSA progression, radiographic progression, clinical progression, AE, drug administration issues, other).
11. Patient takes prohibited medications as described in Section 5.1.6 and Section 12.2

For patients that discontinue from the study, the reason for discontinuation should be recorded in the eCRF. Patients that discontinue will have an Early Withdrawal visit 3 months after the last administration of ELIGARD[®] for safety assessment. At the end of a patient's involvement in this study, the Investigator must ensure that all outstanding data entry is entered in the eCRF unless the patient withdrew consent for their data to be used.

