7.8 Handling of Missing Data, Outliers, Visit Windows, and Other Information

The amount and potential effect of missing data will be explored and detailed further in the SAP. In general, missing data will not be imputed and the data will be analyzed as they are recorded in the study case report forms (CRFs). However, if more than 10% of data is missing for 1 or more key variables, the impact of missing data on the analysis will be discussed, and the pattern of missing data will be explored. If there is evidence of bias in the missing data, and variables that are considered good predictors of the missing data are available, the multiple imputation method at the study level may be used to replace missing values as secondary exploratory analyses. If the multiple imputation method is used, a sensitivity analysis will be carried out comparing results from the complete case analysis (where records with missing data will be dropped) and the full set analysis (with imputed data).

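### Neither HRQoL questionnaire is scheduled at the Early Withdrawal visit, so HRQoL goes unobserved once a patient discontinues, although he is due in clinic

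*Protocol*

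**What the plan says.** HRQoL by QLQ-PR25 and EQ5D-5L is a secondary endpoint, "measured at 0, 6, 12, and 18 months" (Section 2.3.2). The synopsis and Sections 2.2.1 and 5.4 repeat these time points.

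Table 1 has the rows "EORTC QLQ-PR25 (to be measured at baseline, 6 months, 12 months and at 18 months, mandatory" and "EQ5D-5L (to be measured at baseline, 6 months, 12 months and 18 months mandatory". In both, the X stands under Baseline, Month 6, Month 12 and Month 18, and the WD cell is empty. The WD column does carry an X for vital status, reasons for discontinuation, AEs and SAEs, their treatment, and concomitant medication.

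Attendance is expected. Section 6.1 states: "Patients that discontinue will have an Early Withdrawal visit 3 months after the last administration". Footnote m of Table 1 agrees: "A patient who discontinues from the study for whatever reason should have a follow up visit". Both give safety assessment as the purpose. Failure to attend counts as a protocol deviation unless consent was withdrawn. Footnote n limits the Month 18 visit to patients who meet no discontinuation criterion.

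Stopping treatment is itself a discontinuation criterion in Section 6.1, with these example reasons: "PSA progression, radiographic progression, clinical progression, AE, drug administration issues, other". Castration resistance is another.

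Section 7.4.2 summarises HRQoL descriptively by scheduled visit and as change from baseline. Section 7.8 says: "In general, missing data will not be imputed".

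**The concern.** Several of the listed reasons for leaving, such as adverse events and progression, could plausibly go with a change in quality of life. Those patients contribute no HRQoL after they stop, so the Month 12 and Month 18 summaries increasingly describe those who stayed. The study has a single arm, so no comparator would reveal the selection, and Section 1.4 names improved quality of life as an expected benefit.

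The gap is avoidable because the patient is due in clinic anyway. It also has to be closed in the visit schedule: an analysis plan can describe or model missing questionnaires but cannot recover answers that were never asked for.

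**Working it through.** **Plan's own figures.** Section 7.1 assumes a 50% event rate, a 95% interval of ±10 points, a finite population of 10,000 and 10% drop-out.
- n0 = 1.96² × 0.5 × 0.5 / 0.10² = 96.04
- With the finite population correction: 96.04 / (1 + 95.04/10,000) = 95.13, rounded up to 96
- 96 / 0.9 = 106.7, rounded up to 107

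Both 96 and 107 reproduce. The point below does not affect them.

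**Timing.** WD visit = last injection + 3 months.

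| Last injection (month) | WD visit (month) | Questionnaires already due by the last injection | Scheduled HRQoL still to come |
|---|---|---|---|
| 0 | 3 | 0 | 6, 12, 18 |
| 3 | 6 | 0 | 6, 12, 18 |
| 6 | 9 | 0, 6 | 12, 18 |
| 9 | 12 | 0, 6 | 12, 18 |
| 12 | 15 | 0, 6, 12 | 18 |

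Month 15 is the last planned injection. A patient who receives it normally has the Month 18 visit, where both questionnaires are marked, so it is left out. In the rows for Months 3 and 9, the WD visit falls on a nominal HRQoL time, but the WD column does not ask for the questionnaires.

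**Number affected.** 107 × 0.10 = 10.7, about 11 patients by study end. Drop-out of 5% or 20% (assumed range) gives 5.4 or 21.4. Patients who withdraw consent, die or are lost to follow-up must be subtracted; the protocol gives no split.

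**Effect of collecting at WD.** Two assumptions are needed that the documents do not supply: last injections spread evenly over the five rows, and leavers differing from stayers by 10 to 20 points on a 0–100 scale.
- Patients per row: 10.7 / 5 = 2.1. About 2 values map to Month 6 and about 2 to Month 12.
- Shift in each mean: 2.1 / 107 = 0.02, and 0.02 × 10 to 20 points = 0.2 to 0.4 points.
- At 20% drop-out: 21.4 / 5 = 4.3 per row; 4.3 / 107 = 0.04; shift 0.4 to 0.8 points.

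**What stays.** By Month 18 the full 10% is missing. The same assumed difference gives 0.10 × 10 to 20 = 1 to 2 points there. In these five rows no WD value maps to Month 18, so the change leaves that mean as it is and adds a separate end-of-treatment value beside it.

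**The case against.** The strongest reply is that this is a deliberate, consistent design. The WD visit is defined as a safety visit, PSA and testosterone are also unmarked there, and every section gives the same four HRQoL times. That stands: a reader might infer a contradiction, and there is none.

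Second, a patient last injected at Month 3 or 9 who stops at his next injection visit is then at Month 6 or 12. Section 5.4 asks for the questionnaires at those months without reference to a column. This stands in part. Such a patient may complete them, but the protocol does not say which column governs.

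Third, Section 7 requires missing values to be counted. If more than 10% of a key variable is missing, Section 7.8 has the impact discussed and the pattern explored, and it allows exploratory multiple imputation where bias is evident. This makes the gap visible but does not replace the measurement. With 10% planned drop-out the trigger may not be reached.

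A reader might also infer stronger claims that the documents do not support:
- *Leavers vanish from the endpoint.* They keep questionnaires completed before they stop. Only those who stop before the Month 6 questionnaire lack any change value.
- *About half of WD visits coincide with an HRQoL time.* No distribution of withdrawal times is given. Even spread gives 2 of 5, because the Month 15 case normally has its Month 18 visit.
- *Mean change is biased in favour of treatment by a known amount.* Neither the size nor the direction of the leaver–stayer difference is documented. The endpoint is descriptive with no formal comparisons, and scores 3 months after the last injection may reflect later therapy.

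**Conclusion.** The point holds as a minor design weakness. HRQoL is not scheduled from discontinuation onward, even though a clinic visit is already required and exit reasons include adverse events and progression. It concerns at most about 11 of 107 patients at the planned drop-out, fewer once consent withdrawal, death and loss to follow-up are removed.

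Any bias is probably small. The 0.2 to 0.4 points recovered at each of Months 6 and 12 rest on an assumed even spread of last injections and an assumed 10 to 20 point difference. Most of the possible effect lies at Month 18, and collecting at WD does not remove it. The case for changing the schedule is the low cost and the fact that no analysis can supply answers that were never collected.

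**What to change.** - In Table 1, add an X in the WD column for QLQ-PR25 and for EQ5D-5L, and bring footnote m and Sections 2.3.2, 5.4 and 6.1 into line.
- State that a WD value is assigned to Month 6 or 12 when the visit falls within 14 days of that time point, the window already used for scheduled visits. Otherwise report it separately as an end-of-treatment value. In either case, note any therapy started since the last injection.

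The cost is two short paper forms at an existing visit for roughly a tenth of patients, and some scores may reflect later treatment. Sample size, dosing and discontinuation rules do not change.

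One limit remains. The full analysis set in Section 7.2.1 requires post-baseline PSA and testosterone, which are not marked under WD, so some very early leavers may still fall outside the HRQoL summaries.

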1 INTRODUCTION

1.1 Background

Epidemiology of Prostate Cancer

Prostate cancer (PC) is the second most common malignancy in men with nearly 1 million new cases being diagnosed worldwide [Baade et al, 2013]. The analysis of GLOBOCAN data showed that more developed countries have much greater 5-year prevalence and incidence rates than underdeveloped countries [Crawford, 2003].

Approximately 14% of all prostate cancers diagnosed worldwide in 2008 were within the Asia-Pacific region. Differences in prostate cancer incidence rates and prevalence rates exist both regionally within Asia and between Asia and Western nations. The reported incidence of prostate cancer among all cancers affecting men in Asia varies by country; prostate cancer is the third most commonly diagnosed male cancer in Singapore and Malaysia, fourth in Japan and Thailand, fifth in South Korea, sixth in China, and ninth in India [Crawford, 2003]. The overall incidence of, and mortality from, prostate cancer in Asian countries are lower than the rates observed in cohorts of migratory Asians in Western countries, and considerably lower than those in native Western individuals. However, there is an increase in prostate cancer incidence in the Asia-Pacific region, where Hong Kong and Singapore (Chinese population only) recorded annual increases of around 6% for males of all ages between 1998-2009 and 1980-2002, respectively [Baade et al, 2013]. Smaller, but still significant, increases in prostate cancer incidence rates were found for males of all ages in the Philippines and Thailand (3% per year increase between 1983-2002 and 1983-2009, respectively) [Baade et al, 2013].

Prostate cancer is the most common cancer in elderly males. The incidence rates of prostate cancer increase with age. It is relatively rare for prostate cancer to be diagnosed in men <50 years of age, but after this age, the incidence and mortality rates increase exponentially [Baade et al, 2013]. In some Asian countries (Japan, Hong Kong and South Korea) the increase was more pronounced after 60 years of age [Baade et al, 2013]. The majority of cancer cases are diagnosed between 50-79 years of age [Baade et al, 2013].

Prostate cancer rates are highest in Western countries and lowest in Asian countries [Sim & Cheng, 2005]. However, Asian populations generally have higher proportions of men with advanced stage prostate cancer compared with Western populations, despite overall reports of prostate cancer incidence being substantially lower in the former [Ito, 2014]. The epidemiological pattern of prostate cancer in Asia suggests that prostate cancer often goes unnoticed, at least until later stages of the disease, possibly owing to restricted access to screening programs and urology clinics in Asian countries [Ito, 2014].

There was a large disparity in the survival prospects on men with prostate cancer throughout the Asia-Pacific region. Five-year relative survival estimates of 85% and above were reported in New Zealand, Australia, Japan, Singapore and South Korea [Baade et al, 2013]. This contrasts with estimated 5-year survival rates of between 30% to 40% in parts of China and Thailand [Baade et al, 2013].

With the expected increases in life expectancy of men and in the incidence of prostate cancer [Center et al, 2012], the disease's economic burden is also expected to increase substantially. In Europe, it is estimated that the total economic costs of prostate cancer exceed €8.43 billion, with a high proportion of the costs of prostate cancer care occurring in the first year after diagnosis [Mottet et al, 2006]. In European countries with available data (United Kingdom, Germany, France, Italy, Spain, Netherlands), this amounted to €106.7 – 179.0 million for all prostate cancer diagnosed in 2006 [Mottet et al, 2006].

In Asia, the population over 60 years old is about 4 times greater compared to those of North America and Europe [Zhang et al, 2011]. Given that life expectancy is expected to increase markedly in many parts of Asia over coming years, the burden of prostate cancer in this region is likely to increase in the future. Health problems will become a greater burden in Asian countries despite rapid socioeconomic growth.

It has been reported that patients with terminal prostate cancer show considerably decreased quality of life (QoL) for many years before death, owing to the adverse effects of long-term systemic treatments as well as physiological and psychological impairment resulting from progression of local disease and distant metastases [Ito, 2014].

ELIGARD[®] (leuprolide acetate for injection)

ELIGARD[®] (leuprolide acetate) is an established luteinizing hormone releasing hormone (LHRH) agonist that is indicated for the palliative treatment of advanced prostate cancer [ELIGARD local prescribing information, May 2014]. ELIGARD[®] is a long-acting depot formulation that uses Atrigel[®] delivery system (a biodegradable polymer matrix) that allows sustained release of leuprolide acetate following subcutaneous injection. ELIGARD[®] is designed to deliver leuprolide acetate at a controlled rate over a therapeutic period to reduce testosterone levels in men with advanced hormone-dependent prostate cancer. ELIGARD[®] is available in 3 depot formulations of 7.5 mg, 22.5 mg and 45 mg doses for 1-monthly, 3-monthly and 6-monthly administration intervals, respectively.

Study Rationale

Both the safety and efficacy of ELIGARD[®] have been well proven in numerous clinical studies. However, the safety profile of ELIGARD[®] was not established in ethnic Asian populations as no clinical studies of ELIGARD[®] have been conducted in Asia to date. Since data from controlled clinical trials may not necessarily be assumed to apply in their entirety to subpopulations not

studied in those trials, Astellas will conduct this study to establish the safety profile and to confirm the efficacy of ELIGARD[®] in prostate cancer patients in the Asia region. This study will also aim to assess health-related quality of life (HRQoL) of prostate cancer patients using the European Organization for Research and Treatment of Cancer Quality of Life Questionnaire (EORTC QLQ-PR25, prostate cancer disease specific patient reported outcome [PRO]) and EuroQol 5 Dimension 5 Level Health State Utility Index (EQ5D-5L, generic PRO).

This study is a non-mandated Post-authorization safety study (PASS).

1.2 Non-clinical and Clinical Data

Non-clinical data

In all animal studies, serum testosterone was suppressed below or near the castrate threshold (50 ng/dl) within 1 to 3 weeks after a single administration of ELIGARD[®]. Following a single administration, the duration of testosterone suppression to below castrate threshold was > 91 days with ELIGARD[®] 22.5 mg.

Pharmacokinetic studies with ELIGARD[®] 22.5 mg established near complete release of leuprorelin acetate by Day 106. Two of 3 studies with ELIGARD[®] 22.5 mg suggest that a smaller proportion of the total leuprorelin dose is released initially (i.e., 19 - 41% and 22%, respectively).

In single-dose toxicity studies, no untoward systemic or clinical effects (except for the desired pharmacodynamic outcome) have been observed for ELIGARD[®]. Similarly, repeated administration of ELIGARD[®] is not associated with overt toxicity other than that related to the pharmacological action of the active ingredient, leuprorelin acetate.

No acute systemic effects were observed in any of the studies performed with the delivery system (with or without leuprorelin acetate), following single-dose or repeated administration. However, in a chronic toxicity study with ELIGARD[®] 22.5 mg (LEU_PTX_0220), the delivery system control was found to cause mild histopathological lesions in the testis, the epididymis, the prostate, and the coagulating gland as observed with the test article, which were exaggerated when the active product was given at the high dose level (500 µl/kg, i.e., 100 times the human clinical dose).

Details of preclinical data are summarized in the ELIGARD[®] Investigator's Brochure, Edition 5, dated 26th June 2008 and the approved Summary of Product Characteristics.

Clinical data

Response to ELIGARD[®] should be monitored by measuring serum concentrations of testosterone and prostate specific antigen (PSA) periodically [ELIGARD local prescribing information, May 2014]. Majority of patients have increased testosterone levels above baseline during the first week, declining thereafter to baseline levels or below by the end of the second or third week

[ELIGARD local prescribing information, May 2014]. The patients generally achieve testosterone ‘castration levels’ (< 50 ng/dL) within 2 to 6 weeks after the start of ELIGARD® treatment, and the effects are reversible upon discontinuation of drug therapy [ELIGARD local prescribing information, May 2014].

Furthermore, up to 98% of patients showed levels which are less than 20 ng/ dL, comparable to those resulting from surgical bilateral orchidectomy [Berges & Bello, 2006]. This is clinically important because low serum testosterone (<20 ng/dL) within the first year of Androgen Deprivation Therapy (ADT) has been suggested to correlate with improved survival and duration of response to androgen deprivation in men being treated with ADT [Klotz et al, 2015]. The European Association of Urology Guidelines for Prostate Cancer acknowledges that better results are repeatedly observed with lower testosterone levels compared to 50 ng/dL[Mottet et al, 2006]. As with other gonadotropin releasing hormone (GnRH) agonists, ELIGARD® 22.5 mg causes a transient increase in serum concentrations of testosterone (also known as ‘tumor flare’ or ‘testosterone surge’) during the first week of treatment [ELIGARD local prescribing information, May 2014]. Patients may experience worsening of symptoms or onset of new signs and symptoms during the first few weeks of treatment, including bone pain, neuropathy, hematuria or bladder outlet obstruction [ELIGARD local prescribing information, May 2014]. Potential exacerbations of signs and symptoms of the disease in patients with vertebral metastases and/or urinary obstruction or hematuria, may lead to neurological problems such as weakness and/or paresthesia of the lower limbs or worsening of urinary symptoms [ELIGARD local prescribing information, May 2014]. Patients at risk should be closely monitored during these first 2 weeks of therapy and managed as appropriate. Short term anti-androgen therapy may ameliorate these symptoms.

The safety of all ELIGARD® formulations was evaluated in clinical trials involving patients with advanced prostate cancer. The most commonly reported adverse reactions are hot flashes, nausea, malaise and fatigue and transient local irritation at the site of injection. Mild hot flashes occur in approximately 58% of patients[ELIGARD 22.5 mg, Summary of Product Characteristics 2015]. Hyperglycemia, an increased risk of developing diabetes and cardiovascular diseases such as myocardial infarction, sudden cardiac death and stroke have been reported in men receiving GnRH agonists [ELIGARD local prescribing information, May 2014]. It is important to monitor patients’ blood glucose level and cardiovascular condition and manage according to current clinical practice. Decreased bone density and rare cases of pituitary apoplexy (a clinical syndrome secondary to infarction of the pituitary gland) have been reported during post-marketing experience after the administration of GnRH agonists [ELIGARD local prescribing information, May 2014]. Convulsions and QT prolongation have also been reported in the post-marketing setting [ELIGARD local prescribing information, May 2014].

ELIGARD® is contra-indicated in patients with hypersensitivity to GnRH, GnRH agonists or any of the components of ELIGARD® [ELIGARD local prescribing information, May 2014].

The pre-clinical and clinical data are summarized in the ELIGARD® Investigator's Brochure, Version 5, dated 26 June 2008 [ELIGARD Investigator's Brochure, June 2008] and the approved Summary of Product Characteristics [ELIGARD 22.5 mg, Summary of Product Characteristics 2015].

